9. STUDY CONDUCT

9.1. Investigator and Site Selection

9.1.1. Investigator Selection Criteria

The role of the Principal Investigator is to implement and manage the day-to-day conduct of the Study at the investigational site as well as ensure data integrity and the rights, safety and well-being of the subjects involved in the Study. The Principal Investigator is responsible for assuring the Study is conducted according to all protocol requirements and applicable regulations. Refer to **Section 13.3** for more information on Principal Investigator responsibilities.

The following requirements will be evaluated for each Principal Investigator considered for participation in the Study:

- Interest in participating in medical device studies
- Experience conducting clinical studies

- Expertise in performing TIPS procedures
- Availability to oversee study execution
- No conflicts of interest

9.1.2. Site Selection Criteria

The following requirements will be evaluated for each clinical Site considered for participation in the clinical Study:

- Experience of site staff in conducting clinical studies
- Adequate resources (including study coordinator(s), facilities, and administrative support) for the total duration of the study
- Site has the capacity to recruit enough qualified subjects for the study
- Computer with internet access for EDC system (ensuring authorized access in case of firewall)

9.1.3. Investigator Qualifications

A copy of the current medical license and Curriculum Vitae (CV) will be obtained from all Investigators participating in this clinical study as listed on the study delegation log. The CV should be an up to date signed and dated document evidencing any required qualifications and including the Investigator's current position at the investigational site. The signature on the CV must be dated within two years of site activation.

9.2. Site Initiation

Prior to the initiation of this clinical study, each Principal Investigator will approve the protocol by signing the signature page which confirms that the clinical study will be performed in compliance with the current protocol.

A Site Initiation Visit (SIV) will be conducted by the Sponsor or designee in-person or via teleconference to ensure proper training of the investigational site staff participating in the study, including principal Investigators, Sub-Investigators, study coordinators and any other site personnel pivotal to the conduct of the clinical study prior to enrollment of the first study subject. Training will include at least the following: procedures outlined in this protocol, key principles of Good Clinical Practices for Medical Devices (ISO 14155), instructions on completion of the case report forms (eCRF), content of the Investigator Site File, safety reporting, and management of device deficiencies.

Once all required site training and required documentation has been received, reviewed, and approved, the Sponsor or designee will issue written approval of site activation to the Principal Investigator to begin study enrollment.

9.3. Additional Site Staff Activation

Any additional site staff added to the study after the site initiation will receive an individual written approval from the Sponsor or designee once their training and other required documentation have been received, reviewed, and approved.

9.4. Site Staff Training Requirements

Prior to investigational site activation or subsequent involvement in clinical study activities, the Sponsor or designee will provide study training relevant and pertinent to the involvement of the Site staff conducting Study activities.

Study staff training must be documented on a written training record, including at a minimum: the training content, the date of the training, and the trainee's signature.

In the case of non-compliance with the study protocol or other study requirements, study staff may be retrained on pertinent information or documents. Re-training must also be documented on a written training record, including at a minimum: the training content, the date of the training and the trainee's signature.

9.5. Clinical Study Materials and Clinical Study-Specific Equipment

The Sponsor or designee will provide necessary study documentation (e.g., Investigator Site File, eCRF access, Study worksheets, etc.) to the investigational site. The investigational site staff are responsible to acknowledge receipt to the Sponsor or designee after receipt. Computer and internet access is required and is a pre-requisite for site participation.

9.6. Study Device Supply and Accountability

9.6.1. Supply of Devices

The Scorpion Portal Vein Access Kits and the Cook Transjugular Liver Access Sets are marketed products. The devices used in this study will be "off the shelf". No special labeling is required for the devices used in the study. Marketed devices are identified with part and lot numbers included in the device packaging and labeling that will be recorded as part of the study data collection.

9.6.2. Device Storage and Accountability

Devices will be stored according to the requirements described in the current Scorpion set or Cook set IFU. No study-specific device accountability processes are required for this study.

9.6.3. Device Return Procedures

Not applicable. Investigational sites will dispose of used devices in accordance with the labeling and their institution policies.

9.7. Study Closure and Early Termination

9.7.1. Routine Study Closure

When investigational sites are ready to be closed, the Principal Investigator will be notified by the Sponsor or designee. Appropriate notification to IRBs and regulatory authorities, as applicable, will also occur.

A study close-out visit (COV) will be conducted for each site. The purpose of the COV is to collect all outstanding study documents, ensure that the Investigator Site File is accurate and complete, review record retention requirements with the Principal Investigator, and ensure that all applicable requirements are met for the study.

After study closure at the site, the follow up medical care for subjects will continue as per standard of care at the institution.

9.7.2. Early Termination

The Sponsor has the right to terminate the study at any time. Situations that could warrant study termination include, but are not limited to:

Increased incidence of adverse experiences and/or the severity of such, suggestive of a potential, device-related health hazard

Insufficient subject enrollment

Recurrent protocol non-compliance, violations, or deviations

Inaccurate, incomplete, and/or untimely data recording (>2 business days) on a recurrent basis

Lack of cooperation with monitoring visits (e.g., failure to adequately prepare for visits, address action items from one visit to the next, or provide access to medical records)

If the Sponsor suspends or terminates the study prematurely, the Sponsor will send a report outlining the circumstances to the IRBs, regulatory authorities as applicable, and all Principal Investigators. Notification of suspension or termination will occur no later than 5 business days after the Sponsor makes the determination. The Principal Investigator should follow subjects per standard of care at the institution.

The Sponsor reserves the right to terminate an Investigator and/or an investigational site for any of the following reasons:

Repeated failure to secure subject informed consent including protection of personal data prior to enrollment.

Failure to report safety events in a timely manner.

Failure to report serious adverse device effects within 24 hours of discovery.

Repeated protocol deviations.

Repeated failure to complete case report forms.

Failure to enroll an adequate number of subjects.

The Principal Investigator may terminate the study at his site at any time. If the Principal Investigator chooses to terminate the study at his site, close out procedures will be arranged on an individual basis after review and consultation by both parties. In terminating the clinical study, the Sponsor and the Principal Investigator will assure that adequate consideration is given to the protection of subjects.

Clinical Investigation Plan (CIP)

CP-2023-001: Achieving Portal Access with Scorpion Post-Approval Study

Revision: C

Argon Location: All Sites

A suspended or terminated Study may not be reinitiated without approval of the reviewing IRBs, and regulatory authority, as applicable.

10. ADVERSE EVENTS, ADVERSE DEVICE EFFECTS AND DEVICE DEFICIENCIES

10.1. Definitions

The definitions and reporting requirements described in this section cover the requirements outlined in ISO 14155:2020.

10.1.1. Adverse Event

An adverse event (AE) is any untoward medical occurrence, unintended disease or injury, or untoward clinical signs (including abnormal laboratory findings) in subjects, users, or other persons, whether related to the investigational medical device and whether anticipated or unanticipated.

This definition includes events related to the investigational medical device or the comparator; events related to the procedures involved.

10.1.2. Serious Adverse Event

A serious adverse event (SAE) is an adverse event that leads to any of the following:

- a) death
- b) serious deterioration in the health of the subject, users or other persons as defined by one or more of the following:
 - a. a life-threatening illness or injury, or
 - b. a permanent impairment of a body structure or a body function including chronic diseases, or
 - c. in-patient or prolonged hospitalization, or
 - d. medical or surgical intervention to prevent life-threatening illness or injury or permanent impairment to a body structure or a body function
- c) fetal distress, fetal death or a congenital abnormality or birth defect including physical or mental impairment

Planned hospitalization for a pre-existing condition, or a procedure required by the protocol, without serious deterioration in health, is not considered a serious adverse event.

10.1.3. Device Deficiency

A device deficiency is an inadequacy of a medical device with respect to its identity, quality, durability, reliability, usability, safety, or performance.

Device deficiencies include malfunctions, use errors, and inadequacy in the information supplied by the manufacturer including labelling. This definition includes device deficiencies related to the investigational medical device or the comparator.

10.1.4. Serious Health Threat

A serious health threat is a signal from any adverse event or device deficiency that indicates an imminent risk of death or a serious deterioration in the health in subjects, users, or other persons, and that requires prompt remedial action for other subjects, users, or other persons.

This includes events that are of a significant and unexpected nature such that they become alarming as a potential serious health hazard or possibility of multiple deaths occurring at short intervals.

10.1.5. Adverse Device Effect

An adverse device effect (ADE) is an adverse event related to the use of an investigational medical device.

This definition also applies to the comparator medical device and includes:

adverse events resulting from insufficient or inadequate instructions for use, deployment, implantation, installation, or operation, or any malfunction of the medical device.

any event resulting from use error or from intentional misuse of the medical device.

10.1.6. Serious Adverse Device Effect

A serious adverse device effect (SADE) is an adverse device effect that has resulted in any of the consequences characteristic of a serious adverse event as defined in **Section 10.1.2**.

10.1.7. Unanticipated Serious Adverse Device Effect

An unanticipated serious adverse device effect (USADE) is a serious adverse device effect which by its nature, incidence, severity, or outcome has not been identified in the current risk assessment.

10.2. Causality

Each adverse event will be classified according to one of four different levels of causality to the study device and/or procedure:

Not related

Possible

Probable

Definite

Not related: relationship to the device, comparator or procedures can be excluded when:

- the event has no temporal relationship with the use of the investigational device or the procedures to application of the investigation device
- the adverse event does not follow a known response pattern to the medical device (if the response pattern is previously known) and is biologically implausible

- the discontinuation of medical device application or the reduction of the level of activation/exposure - when clinically feasible - and reintroduction of its use (or increase of the level of activation/exposure), do not impact on the serious adverse event
- the event involves a body-site or an organ that cannot be affected, the adverse event can be attributed to another cause (e.g., an underlying or concurrent illness/ clinical condition, an effect of another device, drug, treatment, or other risk factors)
- the event does not depend on a false result given by the investigational device used for diagnosis¹, when applicable
- harms to the subject are not clearly due to use error
- the event depends on a false result given by the investigational device used for diagnosis¹, when applicable

Possible: the relationship to the investigational device or comparator or the relationship to the study procedure is weak but cannot be ruled out completely. Alternative causes are also possible (e.g., an underlying or concurrent illness/ clinical condition or/and an effect of another device, drug, or treatment). Cases where relatedness cannot be assessed, or no information has been obtained should also be classified as possible.

Probable: the relationship to the investigational device or comparator or the relationship to the study procedure seems relevant and/or the event cannot reasonably be explained by another cause.

Definite: the adverse event is associated with the investigational device, comparator, or study procedure beyond reasonable doubt when:

- the event is a known side effect of the product category the device belongs to or of similar devices and procedures
- the event has a temporal relationship with investigational device use/application or procedures
- the event involves a body site or organ that
 - the investigational device or procedures are applied to
 - the investigational device or procedures have an effect on
- the adverse event follows a known response pattern to the medical device (if the response pattern is previously known)
- the discontinuation of medical device application (or reduction of the level of activation/exposure) and reintroduction of its use (or increase of the level of activation/exposure), impact on the event (when clinically feasible)
- other possible causes (e.g., an underlying or concurrent illness/ clinical condition or/and an effect of another device, drug, or treatment) have been adequately ruled out
- harm to the subject is due to error in use

¹ If an investigational device gives an incorrect diagnosis, the subject might, for example, receive an unnecessary treatment and incur all the risks that accompany that treatment, or might be incorrectly diagnosed with a serious disease. In other cases, the subject might not receive an effective treatment (thereby missing out on the benefits that treatment would confer) or might not be diagnosed with the correct disease or condition.

- the event depends on a false result given by the investigational device used for diagnosis², when applicable

To establish the relatedness, not all the criteria listed above might be met at the same time, depending on the type of device/procedures and the serious adverse event.

The Sponsor and the Principal Investigators will distinguish between the serious adverse events related to the study device and those related to a study-specific procedure(s).

An adverse event can be related both to the procedure and the study device. If a causal relationship is established, the adverse event can be classified as an adverse device effect. Complications caused by concomitant treatments not imposed by the protocol are Not related. Similarly, several routine diagnostic or subject management procedures are applied to subjects regardless of the protocol. If routine procedures are not imposed by the protocol, complications caused by them are also considered not related.

In some cases, the event may not be adequately assessed because information is insufficient or contradictory and/or the data cannot be verified or supplemented. The Sponsor and the Principal Investigators will make the maximum effort to define and categorize the event and avoid these situations. Cases where event relatedness cannot be assessed, or no information has been obtained should be classified as "possible".

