6.4.3. Secondary and Exploratory Endpoints

The secondary and exploratory endpoints of this clinical study are outlined in **Table 5**.

TABLE 5. OVERVIEW OF SECONDARY AND EXPLORATORY ENDPOINTS

Endpoint	Description / Definition
Secondary Endpoints	
Portal Vein Access (PVA) time	Time (in minutes) from initial needle throw to portal vein access as confirmed by portogram
Technical success	Creation of a shunt (stent bridging) between the portal and systemic veins
Number of needle passes	Count of needle throws between the hepatic and portal vein to create the parenchymal tract
Procedure duration	Interval (in minutes) from first jugular access for TIPS creation to removal of catheters from subject
Fluoroscopy time	Measured in minutes
Device-related complications	Incidence of complications related to the device as judged by the Principal Investigator
Exploratory Endpoints	

Change in MELD score	Change in score from Screening to Day 30
Change in Child-Pugh score	
Radiation dosage	Measured in air kerma (mGy)
Contrast volume used	Measured in mL
Length of Hospital Stay	Measured in days
Number of ICU days	Measured in days
Change in HPVG	Measured in mm Hg

MELD = Model for End-Stage Liver Disease; ICU = Intensive Care Unit; HPVG = Hepatic Venous Pressure

Gradient

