10.4.1. Anticipated Adverse Events

The following adverse events may occur and are typically associated with the TIPS procedure:

² If an investigational device gives an incorrect diagnosis, the patient might, for example, receive an unnecessary treatment and incur all the risks that accompany that treatment, or might be incorrectly diagnosed with a serious disease. In other cases, the patient might not receive an effective treatment (thereby missing out on the benefits that treatment would confer) or might not be diagnosed with the correct disease or condition.

Hepatic encephalopathy
Infection/Sepsis
Liver failure
Contrast induced nephropathy
Allergic reaction to contrast utilized intra-procedurally
Adverse reactions associated with administration of general anesthesia or conscious sedation
Death

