10.5. Reporting Requirements

10.5.1. Site AE Reporting Requirements

Adverse event reporting will start at the time of the TIPS procedure (on Day 0). Adverse events that occur between the signing of the informed consent form and the initiation of the TIPS procedure will not be reported on the eCRF. Underlying diseases are not reported as adverse events unless the condition worsens or re-appears. Adverse event information, including but not limited to the occurrence date, the reported date, procedures, and medications must be recorded in the subject's medical record and reported as part of the study adverse event report. Adverse event information will be collected for all subjects and assessed at every encounter with the subject.

The AE information submitted on the eCRF should include where possible:

Severity of the event
Causality of the event (in relation to the device and/or procedure)
Seriousness of the event
Outcome of the event

Adverse events should be reported by the site on the appropriate eCRF in the EDC system in a timely fashion from discovery by the site.

Serious Adverse Events and Adverse Device Effects must be reported to the Sponsor or designee within 5 working days by the Principal Investigator or designated study staff of discovery.

It is also the responsibility of the Principal Investigator or designee to inform the IRB of adverse events as required per the IRB policies and procedures and, because the study devices are commercially available, Principal Investigators must comply with any institutional user reporting requirements.

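### The plan specifies one pooled device-or-procedure causality grade per adverse event, so the device-related complications endpoint could take in procedure-only events, and after a change of set no rule assigns an event to either set

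*Combined protocol and SAP*

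**What the plan says.** **Causality scale (10.2).** "Each adverse event will be classified according to one of four different levels of causality to the study device and/or procedure". The definitions pool the sources as well. An event is graded *Possible* when "the relationship to the investigational device or comparator or the relationship to the study procedure is weak but cannot be ruled out completely"; *Probable* and *Definite* can likewise be met through the device, the comparator or the procedure. Events that cannot be assessed default to *Possible*, again with no source named.

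**Data item (10.5.1).** The adverse event information to be submitted lists "Causality of the event (in relation to the device and/or procedure" as one entry.

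**Separation for serious events (10.2).** The sponsor and investigators "will distinguish between the serious adverse events related to the study device and those related to a study-specific procedure(s". No such requirement is stated for non-serious events.

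**Adverse device effect.** Section 10.1.5 gives the definition: "An adverse device effect (ADE) is an adverse event related to the use of an investigational medical device", and extends it to the comparator. Section 10.2 adds: "If a causal relationship is established, the adverse event can be classified as an adverse device effect".

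**Endpoint (6.4.3, Table 5).** Device-related complications are a secondary endpoint: "Incidence of complications related to the device as judged by the Principal Investigator". No level of seriousness is set.

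**Change of set.** Section 8.3 allows a change to the other manufacturer's set and has that use recorded. Section 11.3.1 keeps these cases in the intent-to-treat set, which is also the safety set (11.3.3). Section 11.3.3 bases device-specific post-operative safety on the primary effectiveness set, which by 11.3.2 holds only successes that needed no alternative device.

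**The concern.** The primary safety endpoint (6.4.2) deliberately counts complications of either the procedure or the device. Device-related complications is the one secondary endpoint meant to isolate harm from the access set. It needs a device-only judgment on every complication, but the only causality record the plan describes is one in which a device link and a procedure link earn the same grade. *Probable* does not say what the event is probably related to.

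If the endpoint were compiled from that record, complications of the procedure alone, which should be about equally common in both groups, would dilute any difference between the sets. The loose sentence in 10.2 could have a similar effect on the count of adverse device effects, and those carry a 5-working-day reporting duty under 10.5.1. After a change of set, an event may stem from the first set's passes, the second set or the procedure, and nothing says how to record which.

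The study is open-label (7.8), relatedness is the investigator's call, and the data are meant to support a CE mark application (Sections 3 and 3.3). Attribution not captured at the time is hard to reconstruct later.

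**Working it through.** The point concerns wording, and the plan states no figure that could be reproduced. The passages are compared first; the arithmetic that follows is for scale only.

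**1. Can the endpoint be derived from the specified record?**

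| Event | Device and procedure separated? | Device-only count derivable? |
|---|---|---|
| Serious, one manufacturer's set used | Yes, required by 10.2 | Yes |
| Non-serious, one manufacturer's set used | Not required; pooled grade in 10.2 and 10.5.1 | Not from the grade |
| Any event, both manufacturers' sets used | Only if serious, and then device against procedure, not set against set | Not by set |

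Table 5 covers all three rows.

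**2. Does the adverse device effect label fill the gap?** Section 10.1.5 ties the label to use of the device. The sentence in 10.2 names no object for the causal relationship. The label is therefore clear under 10.1.5 and open under 10.2.

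**3. Does another rule fill it?** Section 10.2 also treats complications of routine procedures that the protocol does not impose as not related, and Section 5.2 describes the study's procedures as within standard of care. One investigator could therefore grade a complication of TIPS alone as not related, and another as definite. The rule adds spread rather than settling the question.

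**4. Which analysis set applies?** Section 11.3.1 assigns overall device safety to the intent-to-treat set, and 11.3.3 assigns device-specific post-operative safety to the primary effectiveness set. Device-related complications fits either description. In the first, cases with a change of set are present with no attribution rule. In the second they are absent, and so are any events from the failed passes that led to the change.

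**5. Scale.** Inputs: 30 subjects per group (6.6), and 3.6% puncture-related complications with the Cook sets (3.2). The second is a literature rate, not a forecast of this endpoint.

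- Expected events per group: 30 × 0.036 = 1.08.
- Probability of none: 0.964^30 = 0.333.
- Probability of exactly one: 30 × 0.036 × 0.964^29 = 0.373. Probability of two or more: 1 − 0.333 − 0.373 = 0.294.
- One event more or fewer: 1/30 = 3.3 percentage points. From 1/30 to 2/30 the estimate goes from 3.3% (exact 95% interval 0.1% to 17.2%) to 6.7% (0.8% to 22.1%).

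**6. Upper limit.** If every procedure-only event were counted, and these were independent of device events with risk q, the observed rate would be 1 − (1 − 0.036)(1 − q). The documents give no q. For assumed values of 5%, 10% and 20% the results are 8.4%, 13.2% and 22.9%. These are ceilings under full absorption, not predictions.

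**The case against.** The strongest reply is that the endpoint is not built from the 10.2 grade at all. Table 5 makes it the investigator's own judgment of device relatedness, and no section derives it from the four-level scale or the adverse device effect label. **This stands.** A reader might infer that the endpoint does absorb procedure-only events; the documents support only that it could. What remains is that no other field for that judgment is described.

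Second, Section 10.2 requires device and procedure to be separated for serious events, which covers many of the weightiest complications. **This stands** and confines the device-versus-procedure gap to non-serious events.

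Third, a reader might infer that any established causal link turns an event into an adverse device effect. **The text does not support that.** The sentence is permissive, follows one about events related to both procedure and device, and sits beside the explicit definition in 10.1.5. It is loose wording that needs aligning.

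Fourth, a reader might infer that the responsible set can never be identified after a change. **That is also too strong.** Section 8.3 records the access device and any alternative set, and 11.3.3 keeps these cases out of device-specific post-operative safety. What is missing is a rule for attributing events when they are analysed in the intent-to-treat or safety set.

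Fifth, Section 10.4 lists procedure-associated events ("The following adverse events may occur and are typically associated with the TIPS procedure") apart from device effects. This helps judgment but does not attribute an actual event.

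Finally, the eCRF is not among the documents and may already hold separate fields. That is possible; the plan should then say so.

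**Conclusion.** The concern holds in limited form. As specified, the causality grade cannot supply a device-only count for non-serious events, the adverse device effect sentence in 10.2 is looser than 10.1.5, and no rule attributes events to the first or second set in cases that remain in the intent-to-treat and safety sets. Device-related complications could therefore include procedure-only events. The documents do not show that they will.

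The size cannot be fixed from the documents. With about one expected event per group at 3.6%, a single misattribution shifts a group by 3.3 percentage points and can double its observed rate. That rests on the literature rate being of the right order for this endpoint. The higher rates in the working rest on assumed procedure-only risks and full absorption. No formal hypothesis is tested, so what is at stake is whether the descriptive device-safety result can be interpreted, not a test decision. The change is worth making before data collection.

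**What to change.** 1. In 10.2 and 10.5.1, record for every adverse event, serious or not, two separate four-level items: relatedness to the access set and relatedness to the TIPS procedure. Restate each grade's definition for one source at a time.
2. Where both manufacturers' sets were used, record relatedness to each set. One device item is enough in all other cases, because the set used is already recorded.
3. Reword the adverse device effect sentence in 10.2 so that only a causal relationship to a device makes an event an adverse device effect, in line with 10.1.5.
4. In 6.4.3 or Section 11, state that device-related complications is derived from the device item(s), which grades count as related, which analysis set is used, and how events in cases with a change of set are counted.

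**Cost:** a few extra eCRF fields, some reworded sentences and a short addition to site training. No added visits or staff. If the eCRF already separates these items, only the text changes.
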